## **9.2 Methods and Timing for Assessing, Recording, and Analyzing Safety Parameters**

For this single-site minimal risk intervention pilot study, the study staff and principal investigator will be responsible for ensuring participants' safety daily and for monitoring and responding to any adverse events or unanticipated problems and for reporting them to the IRB, DSMB, and the NIA Program Officer. No formal safety parameter analyses are planned, but study staff will monitor for differences in pain-related medical visits between the Intervention and Control Arms.

## **9.3 Adverse Events and Serious Adverse Events**

We will monitor for specific unanticipated problems during the study period that might be related to the study intervention. At any time, clinicians can report an adverse event or unanticipated problem potentially related to the study to study staff, the Safety Officer, or the DSMB. We do not expect there to be adverse events directly influenced by the clinical guidance being delivered in this study. All study interventions encourage clinicians to follow well-established national guideline recommendations and known best practices. While the expectedness of adverse events is very low, we will investigate every numerator case identified in all safety measures described above.

As requested by the DSMB, we will perform EHR queries for all patients in the follow-up intervention patient groups (that is, patients having surgery after the one-time study has been delivered to the surgeon intervention and control arms) at approximately postoperative day 14. The purpose of these EHR reviews will be to assess for evidence of uncontrolled pain through review of hospital admissions,

emergency department visits, clinic visits, and patient phone calls/electronic portal messages.

For cases identified by the safety monitoring measures, we will perform manual physician chart review to examine the clinical circumstances and to make a judgment (1) the expectedness of the event (unexpected, expected), (2) the likelihood that the safety event was study related (not related/possibly related/definitely related) and (3) judge the event's severity (abnormal clinical finding without symptoms/symptoms requiring clinical intervention/short term disability or hospitalization/death AND separately define the severity as mild, moderate, or severe).

These will be conducted only by authorized study personnel. Study personnel will interview patients' treating clinicians when needed to obtain additional information. Each case identified will have a case report form with these variables and will be signed and dated by study staff completing the form. These forms will be stored in a locked office. Each adverse event will be given an identification number. If study personnel believe that a patient that experienced an adverse event would benefit from seeing or communicating with their prescribing surgeon, the PI will within 2 business days reach out to this clinician advising them to contact the patient as soon as possible. All study personnel will be trained in HIPAA-compliant procedures. Data will be kept on a password protected drive on a secure network, to which study personnel will have restricted access.

Adverse events will be defined as: Any untoward or unfavorable medical occurrence in a human study participant, including any abnormal sign (e.g., abnormal physical exam or laboratory finding), symptom, or disease, temporally associated with the participants' involvement in the research, whether or not considered related to participation in the research. For this study, we will only be collecting adverse events involving the study interventions, pain, or opioid use. Other post-surgical complications or adverse events will not be captured.

Adverse events will be assessed by a qualified medical professional using the following guidelines to describe severity:

- Mild: Events require minimal or no treatment and do not interfere with the participant's daily activities.
- Moderate: Events result in a low level of inconvenience or concern with the therapeutic measures. Moderate events may cause some interference with functioning.
- Severe: Events interrupt a participant's usual daily activity and may require systemic drug therapy or other treatment. Severe events are usually potentially life-threatening or incapacitating. Of note, the term "severe" does not necessarily equate to "serious".

Additionally, Serious Adverse Events will be defined as any adverse event that: (1)

Results in death; (2) Is life threatening, or places the participant at immediate risk of death from the event as it occurred; (3) Requires or prolongs hospitalization; (4) Causes persistent or significant disability or incapacity; (5) Results in congenital anomalies or birth defects; or (6) Is another condition which investigators judge to represent significant hazards.

Additionally, all Adverse Events and Serious Adverse Events will be assessed for their relationship to study procedures as follows:

- Definitely related: There is clear evidence to suggest a causal relationship, and other possible contributing factors can be ruled out. The clinical event, including an abnormal laboratory test result, occurs in a plausible time relationship to study intervention administration and cannot be explained by concurrent disease or other drugs or chemicals.
- Possibly related: There is some evidence to suggest a causal relationship (e.g., the event occurred within a reasonable time after the trial intervention or patient contact). However, other factors may have contributed to the event (e.g., the participant's clinical condition, other concomitant events).
- Not related: The AE is completely independent of study intervention administration/patient contact, and/or evidence exists that the event is definitely related to another etiology. There must be an alternative, definitive etiology documented by a qualified medical professional.

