#### **4.2 Study Rationale**

Evidence-based postoperative prescribing guidelines have been propagated(7-10) in order to decrease both the number of surgical patients developing new persistent opioid use and the overprescribing of post-surgical opioids. Other nudging techniques like changing electronic medical record prescription size defaults have been used in the surgical setting to decrease opioid prescribing,(11) although such tactics run the risk of increasing opioid prescribing for already-low prescribers.(12)

Despite these initiatives, evidence remains limited regarding the optimal methods for reducing post-surgical opioid prescribing.(13) Our proposed project will test a novel nudging technique that has not been studied in the postoperative opioid prescribing space: direct feedback to surgeons about their patients' opioid prescription-to-consumption ratios. Direct feedback to opioid prescribers after patients suffered a fatal opioid overdose has been shown to reduce subsequent opioid prescribing significantly.(14) We believe that providing granular data to a wide population of surgical prescribers (not just those whose patients overdose) will prove similarly effective. Should our intervention decrease

surgical prescribing, we anticipate it playing a significant role in the national strategy to combat the opioid crisis.

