### 6.3 Study Enrollment Procedures

During the 30-day lead-in period, study *surgeon* participants will be identified through VUMC EMR queries of historical and booked case numbers for the specific procedures listed in section 4.1, above. Given the nature of the planned behavioral nudging intervention, it is not feasible for full consent to be obtained prospectively from surgeon participants as this would very likely affect prescribing behavior in both the Intervention and Control Arms due to the Hawthorne effect. Consequently, we plan to request permission from the VUMC Institutional Review Board to utilize deception for *surgeon* participants, who will be asked to consent for participation in a study giving them information about their patients' opioid consumption (surgeons will be debriefed fully on study purposes upon completion of the study). Surgeon participants will be prospectively selected in a participant log kept by study staff. Surgeons will be randomized on a 1:1 basis to either the Intervention or Control Arms prior to administration of the nudge intervention. Enrolled surgeons must complete a minimum 3 listed cases during the initial 60-day study period (study days #1-60) to be eligible for randomization.

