Study *patient* candidates will be identified through VUMC EMR queries of performed surgical cases for study surgeon participants. All patient candidates including procedures by study surgeons will be sent a pre-recruitment letter by the VUMC Department of Anesthesiology informing them that may be contacted by telephone postoperatively regarding the study. Study team members contacting patients will be blinded to the surgeon randomization assignments. All patient candidates undergoing included procedures by study surgeons and otherwise meeting inclusion/exclusion criteria will be contacted 14 days postoperatively by telephone or electronic messaging and asked to complete an opioid pill count and a brief verbal questionnaire relating to postoperative opioid use and analgesia. Because preoperative or immediate postoperative consenting for the study might affect patient participants' subsequent opioid consumption, we plan to obtain electronic informed consent from *patients* at the time of contact. Study research coordinators will securely document the consent process. Study personnel will also maintain a screening log containing records for all evaluated candidates as well as reasons for study ineligibility and non-participation of eligible candidates.

Additionally, at the request of the study Data and Safety Monitoring Board, a third participant population will comprise *all* patients undergoing surgery *of any kind* by

surgeons in the nudge intervention group for 60 days following receipt of the nudge intervention. This will entail only EHR queries on POD #10 and #30 (on a rolling basis) for pain-related medical concerns and healthcare visits. This is to determine whether surgeon prescribing practices changed sufficiently following nudge relief to compromise postoperative analgesia and potentially harm patients. These patients will not be contacted by study staff unless they otherwise meet inclusion criteria for the study as listed above.

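### Both EHR safety reviews and the between-arm monitoring look only for pain, although section 9.3 puts adverse events involving opioid use in scope

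*Combined protocol and SAP*

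**What the plan says.** All places are in the combined protocol and SAP.

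- **Scope.** Section 9.3 says that "we will only be collecting adverse events involving the study interventions, pain, or opioid use" and that other post-surgical complications will not be captured.
- **Chart review in 9.3.** At about postoperative day 14, staff review admissions, emergency visits, clinic visits, calls and portal messages. "The purpose of these EHR reviews will be to assess for evidence of uncontrolled pain". The parenthesis describing the population refers to follow-up patients of both the intervention and the control surgeons.
- **Query in 6.3.** "This will entail only EHR queries on POD #10 and #30 (on a rolling basis) for pain-related medical concerns and healthcare visits". It covers all patients operated on by "surgeons in the nudge intervention group for 60 days following receipt of the nudge intervention". Its aim is to learn whether prescribing changed enough "to compromise postoperative analgesia and potentially harm patients".
- **Monitoring in 9.2.** No formal safety analysis is planned. Staff watch for differences between arms in pain-related medical visits.
- **Patient contact in 7.1 and 8.2.** Consented patients in both phases answer the COMM-9 misuse measure and questions on satisfaction, amount prescribed, pain visits and refills. Section 11.5 plans pre-post comparisons across groups that include misuse and refills.

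**The concern.** The protocol declares one scope for adverse events and then directs its searches at only part of it. An overdose or an episode of oversedation need not present as uncontrolled pain, so a reviewer following the stated purpose could read the chart and have no instruction to record it.

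The gap carries into reporting. In 9.3, physician chart review starts from cases that the safety monitoring measures identify. In 9.3.1, the quarterly reports list the cases found by the safety measures, and the 48-hour rule for related deaths refers to deaths identified in those measures. If the measures target pain alone, an opioid event has no planned route into that chain through the chart searches.

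What is at stake is how the pilot's safety statement will be read. The background in 4.1 rests on opioid harm. A sentence in the final report saying that no opioid-related events were seen would be taken as evidence, when it would partly be a product of the search rule.

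**Working it through.** The plan gives no rate, margin or power for any safety outcome, so the main check sets the declared scope beside each route by which an event could be found.

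| Route | Section | Patients covered | Target |
|---|---|---|---|
| Chart review, about day 14 | 9.3 | Follow-up patients, both arms | Uncontrolled pain |
| EHR query, days 10 and 30 | 6.3 | All patients of nudge-arm surgeons, 60 days | Pain-related concerns and visits |
| Between-arm monitoring | 9.2 | Both arms | Pain-related visits |
| Visit question | 7.1, 8.2 | Consented patients, both arms | Visits mainly due to pain |
| COMM-9 | 7.1, 8.2, 11.5 | Consented patients, both arms, both phases | Misuse |
| Refills | 7.1, 8.2, 11.4.2, 11.5 | Consented patients, both arms, both phases | Refills after the first prescription |
| Clinician report | 9.3 | Any | Events a clinician thinks may relate to the study |
| Interviews, visits, monitor review | 9.3.2 | Consented patients | Any reportable event that comes to attention |

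1. The first four routes are active and confined to pain.
2. COMM-9 and refills are active and concern opioids. COMM-9 measures misuse, not overdose, sedation or side effects. It reaches only patients who are contacted and consent, and 11.5 itself anticipates that consent may differ by arm after the nudge. It is an exploratory outcome and is not named as a trigger for an adverse event record. Misuse is also absent from the outcome list in 11.4.2, although 1.3, 3.2 and 11.5 name it.
3. The last two routes are passive. No scripted item asks about an opioid adverse effect.
4. So one part of the declared scope, opioid adverse effects other than misuse, has no active search.

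**What a wider search could show.** The plan's figure reproduces: 5 patients per day x 60 days = 300 follow-up patients contacted. Assume an equal split, so 150 per arm, and independent patients. The true event rate p is not in the documents, so a range is shown.

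Chance of at least one event in an arm = 1 - (1 - p)^150:

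- p = 0.2%: 0.26
- p = 0.5%: 0.53
- p = 1%: 0.78
- p = 2%: 0.95

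One-sided 95% upper limit after zero events in 150 = 1 - 0.05^(1/150) = 0.0198, or 2.0%.

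Power to separate 1% from 2% (two-sided 5%, normal approximation): the standard error is sqrt(2 x 0.015 x 0.985/150) = 0.01404 under the null and sqrt((0.0099 + 0.0196)/150) = 0.01402 under the alternative. Power = Φ((0.01 - 1.96 x 0.01404)/0.01402) = Φ(-1.25) = 0.11.

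Patients are clustered within surgeons, so the real information would be somewhat less. On the other side, the 9.3 review covers all follow-up patients, not only those contacted, so the number of charts may exceed 300.

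**The case against.** The strongest defence is that the plan is not blind to opioids. COMM-9 and refills are collected in both arms before and after the nudge, with a comparison across groups planned. Prescribing and consumption are measured in morphine equivalents and can move either way. Patients can say that they received too many pills. Section 9.3.2 commits the team to recording all reportable events on consented patients from discharge to the end of participation, so an opioid event noticed while reading a chart would be recorded for those patients. The purpose sentence in 9.3 does not forbid that. The chart reviews were requested by the DSMB, 9.1 names insufficient opioid as the foreseeable patient risk, and directing effort there is reasonable in a minimal-risk pilot.

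Much of this stands, and it rules out two stronger readings. A reader might infer that opioid-related harm is not searched for in either arm. That is wrong for misuse. A reader might also infer that safety can be judged in one direction only. The two-way measures above do not support that.

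Two further inferences should be resisted. Section 4.2 says "such tactics run the risk of increasing opioid prescribing for already-low prescribers", but the tactics meant are record-system defaults; that feedback would raise prescribing is conjecture. And although "surgeons will be debriefed fully on study purposes upon completion of the study", surgeons consent to a study about their patients' opioid consumption, and clinicians other than study surgeons may also report, so the clinician route is weak but not closed.

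The defence does not supply a targeted search for overdose, sedation or other adverse effects. Incidental recording under 9.3.2 applies to consented patients only. A patient who has died or is incapacitated cannot complete COMM-9.

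**Conclusion.** The mismatch is real and limited. Opioid-use events are in scope, while both EHR reviews and the between-arm monitoring target pain. Outside the exploratory COMM-9 and refill items, opioid-related harm would be found only incidentally or passively, so an absence of such events would be hard to interpret.

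The number of events likely to be missed cannot be stated, because the documents give neither an event rate nor a capture rate. What can be said, assuming 150 independent patients per arm, is that a full search would probably show an event occurring at 1% or 2% at least once in an arm (0.78 and 0.95), and that zero events would exclude only rates above 2.0%. With power of about 0.11 for 1% against 2%, the data would support description and no inference about a difference. The both-arm reading of the 9.3 review rests on its parenthesis. This is a worthwhile, inexpensive alignment and not a flaw in the primary feasibility and acceptability outcomes.

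**What to change.** In 9.3, state the purpose of the both-arm review at about postoperative day 14 as *uncontrolled pain or opioid-related harm*. From the same admissions, emergency visits, clinic visits, calls and messages, record on the same case report form any encounter attributed to an opioid adverse effect, including death. Define that term on the form beforehand so that abstractors apply it alike. Tabulate pain and opioid events side by side by arm from this review, as counts with denominators and without a test.

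The 6.3 query may be widened in the same way. It covers nudge-arm surgeons only, so it cannot supply a between-arm comparison, and the by-arm table will describe events up to about day 14 only.

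The cost is a change of wording, an addition to the form and a little more abstraction time on charts that will already be open. Event counts will be small, and the report should say so.

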### 9.3.1 Reporting Procedures

Should a serious, unanticipated, and possibly or definitely related adverse event, unanticipated problem or safety analysis occur, we will notify the Safety Officer, DSMB Chair, NIA Program Officer, and the VUMC IRB within 48 hours of the study team becoming aware of the event. Our report will include appropriate identifying information for the study, a detailed description of the unanticipated, possibly/definitely related, serious adverse event, and a description of any changes to the protocol or other corrective actions that have been taken or are proposed. If an unanticipated, possibly/definitely related, serious adverse event occurs, we will review relevant clinical decision support and ensure others are not at a greater risk of harm than was previously known or recognized.

Patient deaths related to this study are not expected. However, should we identify a possibly related or definitely related patient death in safety measures described above we will report the death to the Safety Officer, NIA Program Officer, DSMB chair, and the VUMC IRB within 48 hours of our knowledge of the death.

The summary of all SAEs (both anticipated and unanticipated) and safety measures will be reported and shared with the Safety Officer, NIA Program Officer, DSMB chair, and the VUMC IRB quarterly throughout the duration of the project, unless otherwise requested. In addition, the summary for reporting all reportable adverse

events (including a report of all numerator cases to all safety measures identified in this report) will be shared with the Safety Officer, NIA Program Officer, DSMB chair, and VUMC IRB quarterly, unless more frequent reports are requested by the NIA, DSMB, or IRB.

### 9.3.2 Follow-up for Adverse Events

The occurrence of a reportable adverse event (AE) or serious adverse event (SAE) may come to the attention of study personnel during study visits and interviews of a study participant presenting for medical care, or upon review by a study monitor.

All reportable AEs including local and systemic reactions not meeting the criteria for SAEs will be captured on the appropriate case report form (CRF). Information to be collected includes event description, time of onset, qualified medical professional's assessment of severity, relationship to study product (assessed only by those with the training and authority to make a diagnosis), and time of resolution/stabilization of the event. All reportable AEs occurring while on study must be documented appropriately regardless of relationship. All AEs will be followed to adequate resolution.

Changes in the severity of an AE will be documented to allow an assessment of the duration of the event at each level of severity to be performed. AEs characterized as intermittent require documentation of onset and duration of each episode.

The study team will record all reportable events on consented patients with start dates occurring any time post-discharge until the last day of study participation. Events will be followed for outcome information until resolution or stabilization.

## 9.4 Safety Monitoring

For this single-site minimal risk intervention pilot study, the study staff and principal investigator will be responsible for ensuring participants' safety daily and for monitoring and responding to any adverse events or unanticipated problems and for reporting them to the Safety Officer, IRB, DSMB, and the NIA Program Officer. The Data and Safety Monitoring Board (DSMB) will act in an advisory capacity to the NIA Director to monitor participant safety, evaluate the progress of the study, to review procedures for maintaining the confidentiality of data, the quality of data collection, management, and analyses. As the NIA has requested the oversight of a DSMB, we will utilize the oversight of the standing Roybal Centers DSMB. The study team will prepare safety reports quarterly to be reviewed by the NIA and DSMB for recommendations for or against the trial's continuation, as well as any modification to the study. The DSMB will meet at least biannually either in-person or by teleconference call to review study progress, data quality, and participants safety.

